Unanticipated Problems Involving Risk to Subjects or Others

Any incident, experience, or outcome that meets all the following criteria:

- Unexpected in nature, severity, or frequency (i.e., not described in study-related documents such as the IRB-approved protocol or consent form, the investigators brochure, etc.)
- Related or possibly related to participation in the research (i.e., possibly related means there is a reasonable possibility that the incident experience, or outcome may have been caused by the procedures involved in the research.)
- Serious (as defined below) ***“Serious” is different than “severe” as reported in the CTC criteria that applies a grade to the AE.***

Adverse Event

An ***adverse event*** (AE) is any symptom, sign, illness, or experience that develops or worsens in severity during the study. Intercurrent illnesses or injuries should be regarded as adverse events. Abnormal results of diagnostic procedures are adverse events if the abnormality:

- results in study withdrawal
- is associated with a serious adverse event
- is associated with clinical signs or symptoms
- leads to additional treatment or to further diagnostic tests
- is considered by the investigator to be of clinical significance

Serious Adverse Event

Adverse events are classified as serious or non-serious. A ***serious adverse event*** is any AE that is:

- fatal
- life-threatening
- requires or prolongs hospital stay
- results in persistent or significant disability or incapacity
- a congenital anomaly or birth defect
- an important medical event

Important medical events are those that may not be immediately life threatening but are clearly of major clinical significance. They may jeopardize the subject and may require intervention to prevent one of the other serious outcomes noted above. For example, drug overdose or abuse, a seizure that did not result in in-patient hospitalization, or intensive treatment of bronchospasm in an emergency department would typically be considered serious.

All adverse events that do not meet any of the criteria for serious should be regarded as ***non-serious adverse events***.

Adverse Event Reporting Period

The study period during which adverse events must be reported is normally defined as the period from the initiation of any study procedures to the end of the study treatment follow-up. For this study, the study treatment follow-up is defined as approximately 20 weeks following the last administration of study treatment.

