If an infusion is stopped for a subject due to an adverse event or serious adverse event, including but not limited to hypersensitivity reaction/anaphylaxis, no additional study treatment will be given to the study participant who develops the event. Although, the study participant will not receive the investigational product, he or she must be followed for safety purposes according to the protocol.

Study Stopping Rules

This Clinical Trial will stop if any of the following events are present:

1. Subject's Death.
2. Occurrence of any thromboembolic event during or after HB-adMSCs administrations (up to 72 hours).
3. Any cerebrovascular ischemia or seizure event occurring within 72 hours after any of the investigational product administrations.
4. Any Serious Adverse Events determined to be related to the following:

- When there is one CTCAE.v5 grade 4 or 5 AE, irrespective of attribution.
- Either any CTCAE Grade 2 adverse event that persists for more than two weeks, or any Grade 3 adverse event, that occurs within 72 hours after product administration.

Should the study participant discontinue study treatment he/she will be followed for safety according to the protocol safety monitoring plan. The study participant will receive follow up communication via phone calls and/or electronically to ascertain the outcome until resolved fully. All will be documented as per protocol.

All changes to the study stopping rules shall be reviewed by FDA. If the study is suspended for any reason, it will not be re-opened until FDA agrees. Regardless of whether the study is stopped or suspended all subjects will be followed to the EOS as per protocol.

Statistical Methods

Sample size consists of up to 24 subjects who have been diagnosed with Relapsing Remitting Multiple Sclerosis. All data collected from subjects who are enrolled and received the investigational product will be analyzed. The incidence of Adverse Events and Serious Adverse Events will be recorded and reported. Efficacy will be measured by improvement of subject's signs and symptoms associated with Multiple Sclerosis. Interim analysis of all safety and efficacy data may be performed at any time deemed appropriate by the Sponsor. Although, the subject's data may be analyzed at any time, a data analysis of all available data will be conducted when a least 10 subjects in each group have completed Week 24. Data may be analyzed for internal informational purposes, reports, presentations, and manuscripts.

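### Study stopping rule 4 is internally inconsistent on seriousness and attribution, and the product wording of rules 2 to 4 leaves placebo events and the blinded use of rule 2 unsettled

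*Protocol*

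**What the plan says.** The list in the protocol's Stopping Rules, Study Stopping Rules, is introduced by "This Clinical Trial will stop if any of the following events are present". One rule is enough, and stopping is not discretionary. The same section says that a suspended study is not reopened until FDA agrees.

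- Rule 1: "Subject's Death", with no condition on cause or arm.
- Rule 2: "Occurrence of any thromboembolic event during or after HB-adMSCs administrations (up to 72 hours").
- Rule 3: "Any cerebrovascular ischemia or seizure event occurring within 72 hours after any of the investigational product administrations".
- Rule 4, lead-in: "Any Serious Adverse Events determined to be related to the following".
- Rule 4, first bullet: "When there is one CTCAE.v5 grade 4 or 5 AE, irrespective of attribution".
- Rule 4, second bullet: "Either any CTCAE Grade 2 adverse event that persists for more than two weeks, or any Grade 3 adverse event, that occurs within 72 hours" of product administration.

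Under Adverse Events, Definitions, the protocol warns that a serious event is not the same as a severe one "as reported in the CTC criteria that applies a grade to the AE", and it defines seriousness by a separate list of outcomes. The SAP's safety section (5.3.2) says nothing about the stopping rules.

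**The concern.** Rule 4 has two layers that do not select the same events. The lead-in is restricted to serious events and appears to ask for relatedness. The bullets ask for neither, and the first sets attribution aside in terms. The text does not say which layer governs. In a 24-subject trial a single event can end the study, so two people applying the rule in good faith could reach opposite decisions on the same case.

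Rules 2 to 4 also describe the triggering infusion in three ways: HB-adMSCs, investigational product, and simply product. This matters for two reasons. Whether a placebo-arm event counts under rules 3 and 4 is unclear. And rule 2 turns on allocation in a trial where subjects, investigators and site staff are blinded, yet nobody is named to apply it.

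**Working it through.** The documents give no stopping probability or event rate, so there is no planned figure to reproduce. The main check is to run test events through the text.

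**Rule 4.** Assume that the event is not of a type listed in rules 2 or 3, and that any Grade 3 event follows an active infusion. Three readings are possible: (A) the lead-in binds on both seriousness and attribution to treatment; (B) the lead-in binds on seriousness only, because the object of its relatedness phrase is the list and not the product; (C) the bullets stand alone.

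| Event | A | B | C |
|---|---|---|---|
| Non-fatal Grade 4, serious, judged unrelated | no stop | stop | stop |
| Grade 4, not serious, judged related | no stop | no stop | stop |
| Grade 3 within 72 h, not serious, judged related | no stop | no stop | stop |
| Death, judged unrelated | stop (rule 1) | stop (rule 1) | stop (rule 1) |

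The seriousness conflict appears under both A and B. The attribution conflict appears only under A.

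**Product wording.** The Investigational Plan, describing Visit 2, speaks of the first investigational product administration or placebo, which sets placebo apart. The Visit 2 and 6 procedures under Study Visits 1 to 9 put both HB-adMSCs and placebo under investigational product administration. It follows that:

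- A brief Grade 2 seizure within 72 h of a placebo infusion stops the trial under rule 3 if the term includes placebo, and does not if it excludes placebo.
- A serious, related Grade 3 thromboembolic event within 72 h of placebo never meets rule 2. It stops the trial under rule 4 only if product includes placebo.
- A brief Grade 2 thromboembolic event within 72 h that no other rule catches stops the trial in the active arm and not in the placebo arm, on every reading. The decision to stop or continue would then show the site that patient's arm.

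**Illustration of size, on assumed rates.** Inputs: n = 24 subjects (protocol, Investigational Product Assignment); p = chance that a subject has at least one event meeting a rule 4 bullet (assumed 2%, 5%, 10%); s = share of those that also meet the lead-in (assumed 50%). Subjects are taken as independent, and rules 1 to 3 are left out because they apply alongside either reading of rule 4.

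Bullets alone: P(stop) = 1 − (1 − p)^24. Lead-in and bullets together: P(stop) = 1 − (1 − p·s)^24.

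| p | Bullets alone | Lead-in too, s = 50% |
|---|---|---|
| 2% | 1 − 0.98^24 = 38% | 1 − 0.99^24 = 21% |
| 5% | 1 − 0.95^24 = 71% | 1 − 0.975^24 = 46% |
| 10% | 1 − 0.90^24 = 92% | 1 − 0.95^24 = 71% |

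At p = 5%, shares of 25% and 75% give 26% and 60%. If only the roughly 12 active subjects count, the bullets-alone figure at 5% is 1 − 0.95^12 = 46% instead of 71%.

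**The case against.** The best defence of rule 4 is grammatical. Its relatedness phrase points to the list that follows, so it may set no causality test at all; the first bullet would then be the only statement on attribution. That is a fair reading, and it is why the attribution conflict is conditional. It does not remove the seriousness conflict, because the lead-in still says serious and the bullets still do not.

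Three stronger readings are tempting, and the documents do not support them.

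- A reader might infer that rules 2 and 3 contradict each other on arm. They cover different events and are alternatives in one list, so different scopes are possible. The ambiguity lies in the shifting meaning of *investigational product*.
- A reader might infer that rule 2 cannot be applied without unblinding the site. The unblinded pharmacist and the randomization personnel already hold allocation (Controlling Blinded Information), and the medical monitor or DSMB decides whether an adverse event requires unblinding the physician (Blinding for Clinical Evaluators). What is missing is a statement of who applies rule 2. The leak is also narrow: on the broad reading of rule 4, more severe thromboembolic events stop the trial in either arm.
- A reader might infer that the safety rules as a whole are unworkable. Rule 1 is clear, and the sponsor and the investigator may each terminate the trial at any time. The protocol refers to a DSMB, whose operating documents are not available here and might address part of this.

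**Conclusion.** The point holds as an internal inconsistency of wording with real consequences. Rule 4's lead-in and bullets give opposite outcomes for a non-serious Grade 3 event within 72 h and for a non-serious Grade 4 event. If relatedness means attribution to treatment, they also do so for a serious, non-fatal Grade 4 event judged unrelated. Neither the protocol nor the SAP says which text governs. Fatal events are unaffected.

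The product wording is a separate and lesser defect: placebo-arm events have two possible outcomes under rules 3 and 4, and rule 2 needs someone with access to allocation whom the protocol does not name.

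The size cannot be taken from the documents. The contrasts of 38% with 21%, 71% with 46% and 92% with 71% rest on assumed event rates, an assumed share of one half and independent subjects. They show that the choice of reading could matter for the trial's survival. They are not estimates of its chance of stopping.

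**What to change.** 1. Reconcile the lead-in of rule 4 with its two bullets, so that the text states once whether an event must be serious and whether attribution to treatment is required.
2. Reconcile the product wording of rules 2, 3 and 4, with one definition that says whether placebo infusions are included.
3. State which unblinded party, for example the DSMB or medical monitor that the protocol already mentions, applies any rule that depends on arm, and how the decision reaches the site without disclosing allocation.

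The clinical content of each rule is for the sponsor, DSMB and FDA to decide; this point takes no position on it. The cost is a protocol amendment in wording, with the FDA review that the Study Stopping Rules already require and the FDA and IRB agreement required under Protocol Amendments. Sample size and efficacy analyses need not change.

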	<pre> graph TD     subgraph Placebo_Path [Placebo]         direction TB         M[Manufacturer] --- BE[Baxter or an equivalent manufacturer]         BE --- D[20 ml sterile saline]         D --- R[Intravenous]         R --- AR[4-5 ml/min]         AR --- P[Preparation]         P --- PS[Placebo will contain 20 ml of sterile saline. Placebo should be diluted in 250 ml of 0.9% Sodium chloride.]     end      subgraph HBadMSCs_Path [HB-adMSCs (autologous)]         direction TB         H[Hope Biosciences] --- D2[2 x 10^8 ± 20% cells suspended in 20 ml sterile saline]         D2 --- R2[Intravenous]         R2 --- AR2[4-5 ml/min]         AR2 --- P2[Preparation]         P2 --- PS2[Syringe will contain 20 ml of autologous HB-adMSCs. HB-adMSCs should be diluted in 250 ml of 0.9% Sodium chloride.]     end </pre>	
Study Intervention Assignment	
 
Participants will be randomised 1:1 to receive HB-adMSCs active treatment or Placebo.
 
	
Interim Analysis	
 
No interim analysis will be performed in this study
 
	

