### 3.1. Multiplicity Adjustment

The Bonferroni-Holm method for adjustment of multiplicity adjustment is performed for all secondary efficacy endpoint of interest.

Bonferroni-Holm method starts with ordering the p-values in increasing order and starts with testing the hypothesis with the lowest p-value on the  $5/k\%$  level (two-sided), where  $k$  is the number of hypotheses in the procedure. If significant, the testing proceeds to comparing the next lowest p-value with  $5/(k-1)\%$ .

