## 5. STATISTICAL ANALYSES

### 5.1. General Considerations

The final planned primary analyses will be performed after the completion of the following sequential steps:

1. All participants have completed (or withdrawn from) the study as defined in the protocol.
2. All required database cleaning activities have been completed and final database release and database lock has been declared by Data Management.

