#### 5.1.1. General Methodology

Unless otherwise stated, all hypotheses will be tested at a 2-sided significance level of 0.05 and 95% confidence interval. All continuous measurements will be summarised descriptively at each visit by treatment using observed data.

Summary of continuous variables will be presented using N, Mean, 95% confidence interval of mean, Standard Error of mean (SE), Standard Deviation (SD), Median and Range (Minimum and Maximum). The categorical variables will be presented using number and percentage based on N.

For measurements over time mean values will be plotted to explore the trajectory over time. Observed data will be used as the basis for plotting data along with bars as +/- SE, not otherwise specified.

As a primary analysis, a standard Analysis of Covariance (ANCOVA) will be applied for primary and secondary endpoint to test the significance of the effects of the treatment at Week 52. The model includes treatment as fixed factor and the corresponding baseline value as a covariate.

A parametric Repeated Measures Analysis (RMA) Model will be applied as a secondary analysis to test the significance of the effects of the treatment at Week 4, Week 8, Week 16, Week 24, Week 32, Week 42 and Week 52 including baseline as covariate.

Presentation of results from a statistical analysis model will include the estimated mean treatment effects (Least Square Means (LSMeans)). For all endpoints analysed statistically, estimated mean treatment differences will be presented together with two-sided 95% confidence intervals and p-values,

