#### **5.4. Changes to Protocol Defined Analyses**

Analysis is planned as per protocol. No deviation from the planned protocol specified analysis.

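### The protocol requires an analysis at Week 24 that the SAP says will not take place, and neither document protects the 0.05 level or the blind around it

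*Protocol*

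**What the plan says.** Protocol, Statistical Methods, makes three statements. One analysis is mandatory: "a data analysis of all available data will be conducted when a least 10 subjects in each group have completed Week 24". Others are optional: "Interim analysis of all safety and efficacy data may be performed at any time deemed appropriate by the Sponsor". On use of the data: "Data may be analyzed for internal informational purposes, reports, presentations, and manuscripts".

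The SAP says the opposite in section 2.2: "No interim analysis will be performed in this study". Section 5.1 places the primary analysis after a condition that includes "All participants have completed (or withdrawn from) the study as defined in the protocol", and after database lock. Section 5.4 then states: "No deviation from the planned protocol specified analysis".

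On error control, SAP 5.1.1 says that "all hypotheses will be tested at a 2-sided significance level of 0.05". The only multiplicity rule, in section 3.1, is Bonferroni-Holm: "adjustment of multiplicity adjustment is performed for all secondary efficacy endpoint of interest". It does not address repeated looks.

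**The concern.** A SAP cannot cancel a mandatory protocol analysis by omitting it. The protocol's own section on amendments requires any change to be submitted to the IND and agreed by FDA and the IRB first. As the documents stand, a team that follows the protocol performs an analysis that the SAP says does not exist, with no rules for it.

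Two things are at stake. The first is error control. If an early result can be used to claim benefit, or to stop or change the trial, the 0.05 level no longer describes the chance of a false positive. The second is the blind. The primary outcome is a patient-reported questionnaire at one site, and subjects who have just reached Week 24 still have an infusion at Week 32 and assessments at Weeks 42 and 52 ahead of them. Knowledge of early group results could affect what is recorded later.

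**Working it through.** **Step 1. The passages side by side.**

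| Question | Protocol | SAP |
|---|---|---|
| Analysis before the end? | Required at 10 per group, Week 24 | None (2.2) |
| Further looks? | Allowed, no limit | None (2.2) |
| Efficacy included? | Yes for the optional looks; all available data for the required one | Week 52 primary test, after completion and lock (3, 5.1) |
| Boundary or no-claim rule? | None | None |
| Who is unblinded? | Pharmacist and randomization personnel; data analysts are to stay blinded | Not addressed |
| Departure from protocol? | Not applicable | None declared (5.4) |

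The required look and SAP 2.2 conflict, so the statement in SAP 5.4 is incorrect. The SAP also has no population for the look: its efficacy set (section 4) requires all six infusions, and the sixth is at Week 32.

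**Step 2. Reproduce the stated level.** One final test with critical value 1.96 gives 2 × (1 − Φ(1.96)) = 0.0500, as in SAP 5.1.1.

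**Step 3. Error if the Week 24 look could also count as success.** From the documents: two-sided 0.05 at each test, 1:1 allocation, 24 subjects planned, at least 20 at the look. Assumed, because the documents give no value: ρ, the correlation between Week 24 and Week 52 change scores; normal test statistics; all 24 subjects in the final test.

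Overall error = 1 − P(|Z1| < 1.96 and |Z2| < 1.96), bivariate normal with correlation r = ρ × √(20/24) = 0.913ρ.

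| ρ (assumed) | r | Overall error |
|---|---|---|
| 1 | 0.913 | 0.0691 |
| 0.9 | 0.822 | 0.0767 |
| 0.7 | 0.639 | 0.0861 |
| 0.5 | 0.456 | 0.0919 |
| 0 | 0 | 0.0975 |

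The last row can be checked by hand: 1 − 0.95² = 0.0975.

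The protocol sets no maximum number of looks. As an illustration only, equally spaced unadjusted looks including the final one (1,000,000 simulated trials) give about 0.083 for two, 0.107 for three, 0.126 for four and 0.142 for five.

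**Step 4. What would hold the level, for one look plus the final.**

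- The look supports no efficacy claim and no efficacy-based stop or change: the final test stays at 0.05.
- Interim threshold p < 0.001, final 0.05: overall 0.0500 (r = 0.913) to 0.0506 (r = 0.456). At r = 0 it is 1 − 0.999 × 0.95 = 0.05095. The overall error is therefore about 0.050 to 0.051.
- O'Brien-Fleming-type spending at information fraction t (assumed): interim/final p of 0.00009/0.0500 at t = 0.25, 0.0056/0.0478 at t = 0.50, and 0.0318/0.0393 at t = 20/24.

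**The case against.** The strongest reply is that the planned inference is untouched. The hypothesis in SAP section 3 concerns Week 52 only, and it is tested once, after completion and lock. The listed study stopping rules in the protocol are safety rules, and subjects are followed to the end of study even if the trial stops. A Week 52 test always performed at 0.05 keeps its 5% error however often the data are viewed. This stands. A reader might infer that the trial's type I error is already 7% to 10%; the documents do not support that. What remains is that they do not close the route to inflation either. The protocol allows manuscripts without tying them to the final analysis, and its premature termination section lets the sponsor or investigator end the trial at any time with no efficacy or futility criterion.

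A reader might also infer that the Week 24 analysis must compare the arms and unblind the analysts. The text says only that the trigger counts subjects in each group, and the pharmacist or randomization personnel could confirm that count. The one model that the protocol names concerns within-subject change. Nor does any passage say that results will go to site staff, or that publication will precede Week 52. These are possibilities left open, not plans. They still matter because the protocol mentions the DSMB's role in unblinding only for adverse events, and no one is assigned to run an unblinded analysis.

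Finally, the any-time looks are optional, so a SAP that declines them contradicts nothing. That is correct: the direct conflict is with the mandatory look. The optional clause remains in force in the protocol, however, and has no limit.

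**Conclusion.** The contradiction is certain and needs no assumption: the protocol mandates a look, the SAP denies it, and SAP 5.4 certifies that nothing differs. It must be fixed on that ground and because the look has no firewall. The 0.05 level is best described as unprotected rather than inflated. The 6.9% to 9.75% range is conditional on the early result being allowed to count as success or to stop or change the trial, and on the correlation and sample assumptions in Step 3. More looks would raise it, and nothing in the documents caps the number.

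**What to change.** Reconcile the protocol's Statistical Methods section with SAP 2.2 and 5.4, in one of two ways.

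1. **Remove the looks.** Amend the protocol to delete the Week 24 analysis and the any-time efficacy clause.
2. **Keep the Week 24 look and specify it.** State in the SAP its data, endpoint and population. Limit further efficacy looks, which also means amending the open-ended protocol clause. Have an unblinded statistician, separate from the blinded site staff and analysts, run it, and withhold results from the site until Week 52 database lock. Then either state that it supports no efficacy claim or efficacy-based stop, which leaves the final test at 0.05, or set a boundary from Step 4. With spending, the final threshold would be about 0.039 to 0.050, depending on the information fraction.

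Under either route, correct SAP 5.4. The cost is a protocol amendment and some SAP text, plus the loss or restriction of early by-group efficacy data. The no-claim option and the p < 0.001 option leave the final threshold at 0.05; spending can make it stricter.
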